## **C12. Participants: Recruitment, Retention, and Data Collection Procedures**

### **C12a. Clinicians**

**Recruitment.** Participants will be recruited across 12 sites (Clinicians:  $N=187$ ; target:  $N=150$ ) (*Letter of Support*: CEO [name]). The number of sites and clinicians has been determined by a simulation-style power analysis to detect a small effect size predicted by previous research (*C13. Data Analysis Plan*). The main sites have been identified, but not enrolled (*Letters of Support* from regional clinic directors). As there are at least 16 sites from which to select (easily accessible from primary site) and at least 250 eligible clinicians across these sites, we are confident that we can obtain the targeted number of both sites and clinicians. Said differently, even if a site administrator enrolls a site, not all clinicians will need to participate, an important factor to avoid any perception of coercion. Given site diversity, the large number of eligible sites will maximize the likelihood that results will generalize to the broader population of community mental health centers. Sites range in size from 12 to 52 clinicians. Within each enrolled site, clinicians will have the option to participate if they (a) are at least 80% full-time equivalent (b) provide individual psychotherapy to (c) adults with depression (d) in English. These inclusion criteria reflect over 95% of clinicians at the eligible sites. Based on our pilot study, we have experienced that even those who are not supportive of MBC have agreed to participate, therefore making it unlikely that self-selection to participate would limit the generalizability of our sample. During Phase 1 (months 5-8; Table 4), clinician enrollment will begin across all sites and site randomization will occur as site level randomization improves project feasibility and reduces contamination confounds. This decision to randomize by site was also influenced by literature indicating the impact of organizational culture and climate on the implementation process (Aarons et al., 2012; Damschroder et al., 2009), which will be assessed at baseline (AT1).

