implemented using the R lmerTest package with a random intercept for clinic. The b path was assessed using generalized linear mixed models with a logit link function for a binary distribution using the lme4 package. **Aim 3 Hypotheses:** Adapted MBC protocols (i.e., tailored condition) will outperform routine weekly administration of PHQ-9s (i.e., standardized condition) with respect to clinically significant change in depression severity from intake to week 12. Depression severity was analyzed using linear mixed models with Satterthwaite degrees of freedom implemented using the R lmerTest package. Multiple imputation was used to estimate missing values across 20 datasets in which 22.8% of patients did not complete the 12-week interview. We first assessed whether there was a change in PHQ-9 between intake and week 12 in a mixed model containing patient status as a covariate and random intercepts for patient and clinic. Next, implementation group was added to the model. In addition, number of sessions, number of sessions that the PHQ-9 was recorded, and number of sessions that the PHQ-9 was discussed were added to the model. We also examined the interactions between new patient status and the focal variables. **Power calculations.** A power analysis for the multilevel models for Aim 1 was assessed with Monte Carlo studies in which power is the proportion of significant effects (2-tailed  $\alpha$ ,  $p < .05$ ) for parameters of interest observed over repeated analyses of simulated data (Muthén & Muthén, 2002; Thoemmes, Reiser, & MacKinnon, 2010) using MPlus (version 7). For each model, 10,000 data sets were simulated and analyzed. Data in the Monte Carlo studies were simulated with the goal of identifying the smallest detectable effect size with power  $> 80$ . Dropout was simulated to reflect an increase of 5% missing data per wave. Repeated measurements were nested within participants (ICC = .50) and participants were nested in sites (ICC = .05). Average effect sizes for Aim 1 analyses were computed using an approximation of Cohen's  $d$  for growth models (Feingold, 2009). Using this metric, we are sufficiently powered to detect effect sizes as small as  $d = .46$  for the clinician models ( $N = 150$ ) and effect sizes as small as  $d = .30$  for the client models ( $N = 500$ ). For Aim 2, we conducted power analyses for the hypothesized mediation effects with the same assumptions described above but with the use of effective samples size estimates (an ICC corrected sample size) based on a design effect adjustment (Bickel, 2007) in order to use standard effect size metrics. The  $\kappa^2$  effect size for mediation (.01, .09, and .25 represent small, medium, and large  $\kappa^2$  respectively) was computed (Preacher & Kelly, 2011). We are sufficiently powered to detect effect sizes as small as  $\kappa^2 = .16$  for the clinician models and effect sizes as small as  $\kappa^2 = .10$  for the client models. For Aim 3 analyses, we are sufficiently powered to detect effect sizes as small as  $r = .27$  for clinicians and as small as  $r = .21$  for clients. The planned sample sizes are consistently sufficient for detecting medium effect sizes for clinician outcomes and small effect sizes for client outcomes, with the power to treat site as a random effect based 6 sites per condition (Atkins & Baldwin, 2013).

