#### **C14. Potential Problems & Alternative Strategies.**

Our hypothesis is that tailored implementation will outperform the standardized approach. However, it is possible that this hypothesis will not be supported. Findings of this nature would not be undesirable, but rather would illustrate that while emerging research suggests the need to contextualize implementation interventions (Fixsen, 2005; Wallerstein & Duran, 2010), this customization compromises ultimate outcomes—a critical realization for the field of implementation science. Furthermore, if we are unable to detect mediators of implementation and effectiveness outcomes included in this proposal, it may suggest the need to re-evaluate the *Framework of Dissemination*. Specifically, putative mediators of the dissemination and implementation process not included in this model might require empirical investigation. Our qualitative analyses will allow for careful examination of unanticipated mediators. At the level of the clinician, we anticipate substantial variability in competency and general approach to psychotherapy. However, we are not concerned about the effects of this variability on study outcomes because (1) randomization should result in equivalent variability across conditions and (2) MBC is conceptualized as transtheoretically relevant, regardless of the therapist’s orientation or training.

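### The closing power summary is contradicted for Aim 2 by the plan's own kappa-squared benchmarks: the reported minima are .16 (clinicians) and .10 (clients), against .09 for medium and .01 for small

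*Combined protocol and SAP*

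**What the plan says.** All the figures are in the Power calculations part of C13a. The criterion is two-sided 5% significance, and the aim of the simulations is stated as: "Data in the Monte Carlo studies were simulated with the goal of identifying the smallest detectable effect size with power" above 80%.

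- **Aim 1:** smallest detectable d of .46 for clinicians (N = 150) and .30 for clients (N = 500).
- **Aim 2:** "For Aim 2, we conducted power analyses for the hypothesized mediation effects with the same assumptions described above", but using effective sample sizes from a design-effect adjustment. The scale is printed as "01, .09, and .25 represent small, medium, and large" (the first value is .01). The text then gives .16 "for the clinician models and effect sizes as small as" .10 for the client models.
- **Aim 3:** smallest detectable r of .27 for clinicians and .21 for clients.

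The paragraph ends with the summary: "The planned sample sizes are consistently sufficient for detecting medium effect sizes for clinician outcomes and small effect sizes for client outcomes".

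Two other places bear on this. C12a (Recruitment) says: "The number of sites and clinicians has been determined by a simulation-style power analysis to detect a small effect size predicted by previous research", and points to C13. C14 says that "if we are unable to detect mediators of implementation and effectiveness outcomes included in this proposal, it may suggest the need to re-evaluate" the guiding framework, and shortly afterwards adds: "Our qualitative analyses will allow for careful examination of unanticipated mediators". Section A lists Aim 2 as one of two secondary exploratory aims.

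**The concern.** The summary follows the minima for all three aims and claims to hold throughout, so it covers Aim 2. The Aim 2 analysis is described as addressing outcomes at both the clinician and the client level, so both halves of the sentence apply to it. Yet both Aim 2 minima are larger than the effect sizes that the summary says can be detected, on the only one of the three metrics for which the plan prints a scale.

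What is at stake is how a null mediation result is read. C14 treats failure to find mediators as a possible reason to look again at the framework. A reader who relies on the summary would take such a null as evidence against medium clinician and small client mediation effects. The reported minima do not support that.

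A lesser point is one of wording: C12a describes the sizing of sites and clinicians as aimed at a small effect, whereas C13a describes what can be detected for clinicians as medium.

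**Working it through.** **Main check, from printed figures only.** Inputs: benchmarks .01, .09 and .25; Aim 2 minima .16 and .10 (all C13a).

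| Level | Claimed | Benchmark | Reported minimum | Difference | Ratio |
|---|---|---|---|---|---|
| Clinician | medium | .09 | .16 | .16 − .09 = .07 | .16/.09 = 1.78 |
| Client | small | .01 | .10 | .10 − .01 = .09 | .10/.01 = 10 |

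The client minimum also exceeds the medium benchmark: .10/.09 = 1.11.

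**Are the minima plausible, or misprints?** The plan gives neither the mediation test nor the split between the two paths used for power, so exact reproduction is not possible. An approximation needs these assumptions: equal standardised paths a = b, no direct effect, 12 equal sites, site ICC .05 (from C13a), and 0% or 10% loss (my reading of 5% more missing per wave).

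1. Effective sample size = N / [1 + (m − 1) × .05], with m = N/12.
   - Clinicians: m = 12.5, design effect 1.575, 150/1.575 = 95.2. With 10% loss: 89.3.
   - Clients: m = 41.67, design effect 3.033, 500/3.033 = 164.8. With 10% loss: 159.3.
2. Kappa-squared = ab divided by its maximum possible value given the variances and correlations.
3. Standard errors: SE(a) = √[(1 − a²)/(n − 2)]; SE(b) = √[1/(n − 3)] when a = b.
4. Sobel test: z = ab / √[a²SE(b)² + b²SE(a)²], power = Φ(z − 1.96). Joint significance: power = Φ(a/SE(a) − 1.96) × Φ(b/SE(b) − 1.96).

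| | Clinicians | Clients |
|---|---|---|
| Minimum stated in plan | .16 | .10 |
| Minimum at 80% power, Sobel | .150 to .159 | .090 to .093 |
| Minimum at 80% power, joint significance | .103 to .109 | .061 to .063 |
| Power at the stated minimum, Sobel | 80% to 83% | 83% to 84% |
| Power at the claimed size, Sobel | 53% to 56% (at .09) | about 14% (at .01) |
| Power at the claimed size, joint significance | 68% to 72% (at .09) | about 6% (at .01) |

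The Sobel figures come close to the printed minima, so these do not look like misprints. In every variant the clinician minimum stays above .09 and the client minimum stays far above .01. Under joint significance the client minimum lies between the small and medium benchmarks, not above medium.

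**Aims 1 and 3.** C13a prints no small or medium cut-offs for d or r, so the summary's labels cannot be checked for these aims.

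**C12a against C13a.** C12a prints no number. C13a gives d = .46 for clinicians and uses the label medium. The labels differ; no computed quantity does.

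**The case against.** The best defence concerns the clinician half. The plan says that its three values represent small, medium and large; it does not call them lower limits. If medium is a band running from .09 towards .25, then .16 is a medium effect and the clinician claim stands. That is a fair reading. It does not change the fact that an effect at the printed medium value falls below the reported minimum, and it does nothing for the client half, where .10 exceeds both the small and the medium values.

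A second objection is that the minima are not tied to the analysis described. Under Aim 2, C13a tests the path from condition to mediator and the path from mediator to outcome in separate models, the latter a logit mixed model. No test of kappa-squared is described. This stands. A reader might infer that Aim 2 has 80% power only at .16 and .10 or above. The documents do not support so firm a statement: these are the minima that the power analysis reported, and a test closer to separate path tests gives lower values under the assumptions above.

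Third, the consequence is limited. The wording in C14 is tentative, it speaks of studying mediators outside the model, and it keeps a qualitative route open. It is not a decision rule. The true minima and the scale are also printed in the same paragraph as the summary, so nothing is hidden. This lowers the weight of the point but does not make the summary correct.

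On C12a, the sentence covers sites as well as clinicians and refers to an effect predicted by earlier research, which need not equal the minimum detectable effect. The mismatch is therefore editorial.

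**Conclusion.** The closing summary is contradicted for Aim 2 by the plan's own scale. The client half is firm: the reported minimum of .10 is ten times small and just above medium, so small client mediation effects are not detectable at the stated power. The clinician half is conditional: .16 is 1.78 times the medium benchmark, so an effect at that benchmark lies below the reported minimum, but .16 may be called medium if the term is read as a band from .09 to .25. These conclusions rest only on printed figures; the approximate power values rest on an assumed path split and test, and are not needed.

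A reader might go further and infer that the size labels for Aims 1 and 3 are also wrong, or that the trial is too small. The documents support neither: they print no cut-offs for d or r, and the contradiction lies in how Aim 2 power is described. Severity is low, because Aim 2 is secondary and exploratory and nothing in the conduct of the trial depends on the sentence.

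**What to change.** 1. **C13a, Power calculations.** Delete *consistently* and replace the small/medium summary with the reported minima by aim: Aim 1, d = .46 (clinicians) and .30 (clients); Aim 2, kappa-squared = .16 and .10; Aim 3, r = .27 and .21. Add that the power analysis reported Aim 2 minima above the medium benchmark of .09 at both levels, so that small client mediation effects, and clinician mediation effects at the medium benchmark, fall below the reported minima. Attribute these values to the power analysis and do not present them as exact limits of the separate path tests.
2. **C14.** Add a short note that a null mediation result does not exclude effects below these reported minima. Keep the sentence on qualitative analyses.
3. **C12a (editorial only).** Align the description of a small effect with the clinician figure in C13a (d = .46), without attributing .46 to previous research.

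The cost is text edits in three places and a less favourable power statement. Enrolment, conduct and analyses stay as they are.

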**Aim 1: Hypotheses:** Tailored implementation will outperform standardized in terms of (H1a) fidelity. MBC clinician fidelity was evaluated with two variables: (1) whether the PHQ-9 was recorded in the EHR, and (2) among encounters for which the PHQ-9 was recorded, whether it was discussed. Both outcomes were modeled using generalized linear mixed models with a logit link function for a binary distribution using the lme4 package. All models included random intercepts for clinicians and patients. Models for both outcomes were constructed in an identical sequence. Models comparisons in the model-building sequence described below were evaluated using the Bayesian Information Criterion (BIC); the model with the better BIC was selected for presentation. Several unconditional growth models (i.e., models with only parameters for time) were fit (i.e., linear, quadratic, log-transformed number of months). After establishing the unconditional growth model, additional fixed effects were added in the following sequence: (1) group main effect and (2) group x time interaction. Finally, new versus existing patient status was investigated as a main effect using a dummy variable for new patient status and as a patient status x group interaction.

**Aim 2: Hypotheses:** Contextual mediators will be leveraged in the tailored condition, but serve as barriers in the standardized condition. Mediation models were fit to evaluate which contextual factors (based on clinician-completed surveys, Table 5; and, clinician selection of drop-down menu reasons for MBC deviations captured in the electronic health record) mediate the impact of the implementation condition on both clinician- and client-level outcomes. The two critical effects underlying mediation were evaluated in separate models: treatment condition predicts the mediator (path *a*) and the mediator predicts the outcome (path *b*). Specifically, mediators were assessed at the conclusion of the implementation window and the mediators were used to predict PHQ9 completion in the sustainment window. The *a* path was assessed using linear mixed models with Satterthwaite degrees of freedom

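### The plan's own figures contradict its claim of sensitivity to small client effects, and d = .30 is not the detectable effect of the only depression model it writes down

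*Combined protocol and SAP*

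**What the plan says.** Section A (Specific Aims) makes Aim 1 co-primary, with H1a on fidelity and H1b on client depression severity. C12a (Recruitment) says a simulation-based power analysis for a small effect fixed the numbers of sites and clinicians.

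C13a describes that simulation. Repeated measures have an ICC of .50 within participants, and "participants were nested in sites (ICC = .05". Effects are expressed as d for growth models. "Using this metric, we are sufficiently powered to detect effect sizes as small as" d = .46 for clinicians (N = 150) and d = .30 for clients (N = 500).

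For Aim 2 the plan prints a scale for κ²: "effect size for mediation (.01, .09, and .25 represent small, medium, and large". The detectable values are .16 (clinicians) and .10 (clients). "For Aim 3 analyses, we are sufficiently powered to detect effect sizes as small as" r = .27 for clinicians and r = .21 for clients. The summary is "The planned sample sizes are consistently sufficient for detecting medium effect sizes for clinician outcomes and small effect sizes for client outcomes".

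Under Aim 1, C13a lists one hypothesis: "Tailored implementation will outperform standardized in terms of (H1a) fidelity". Depression appears only under Aim 3: "Depression severity was analyzed using linear mixed models with Satterthwaite degrees of freedom". That model is a "mixed model containing patient status as a covariate and random intercepts for patient and clinic. Next, implementation group was added to the model". The only interactions mentioned for it involve new-patient status.

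**The concern.** The summary sentence is what a reader will carry forward, and it does not fit the figures above it. Separately, d = .30 is an Aim 1 client figure with no Aim 1 client model behind it. A reader would naturally attach it to the only depression model in the plan, which tests something else. In that model the group term compares sites on PHQ-9 averaged over intake and week 12, so the site ICC enters its standard error in full.

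What is at stake is how a null result is read. C14 says that failure of the tailoring hypothesis would show that customisation harms outcomes. If the group term had little chance of detecting the effect the plan claims it can detect, a null would not support that statement.

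**Working it through.** **Inputs from C13a and C11:** two-sided α = .05; power 80%; 12 sites, 6 per condition; 500 clients (n = 500/12 = 41.67 per site); 150 clinicians; ICCs .50 and .05. **Assumed:** equal site sizes; two client waves (intake and week 12, per C12b); total variance 1; no dropout unless stated. The detectable effect is 2.802 × SE (normal) or 3.110 × SE (noncentral t, 12 − 2 = 10 df, about what Satterthwaite gives here).

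**1. Wording against figures**

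| Statement | Plan's own figure |
|---|---|
| Small effects for clients (C13a) | κ² = .10; printed medium is .09, small is .01 |
| Small effect set the sites and clinicians (C12a) | d = .46, called medium in C13a |

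**2. Trying to reproduce d = .46 and d = .30.** As a difference in change with no person or site variance in change, individual change variance is V = 2 × .50 = 1.0 and SE = √(4V/N).
- Clinicians: √(4/150) = .1633, giving .457. This matches .46 before dropout. With 5% more missing per wave it becomes .468–.475, depending on the spacing of three assumed waves.
- Clients: √(4/500) = .0894, giving .251, not .30. Raising V to 1.43 gives .30; a small site variance in change would do so too.

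The documents give no waves, tested parameter or variance in change for the simulation, so the two figures cannot be fully reproduced.

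**3. The written group term.** With site variance s, person variance p and residual e, averaged over two waves: SE = √{2[s + (p + e/2)/n]/6}.
- ICC .05 of total variance (s .05, p .45, e .50): √{2[.05 + .70/41.67]/6} = .1492. Detectable: **.418 normal, .464 with 10 df**. Taking p .50, e .45 gives .420 and .466.
- ICC .05 of between-person variance (s .025, p .475, e .50): √{2[.025 + .725/41.67]/6} = .1189. Detectable: **.333 and .370**.
- With unlimited clients, on the first reading, √(2 × .05/6) = .1291, so the floor is .36 or .40.

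Applying the 22.8% missing at week 12 to the first case gives .421 and .468, so missingness matters little for this term.

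**4. What a .30 difference in change does to that term.** With equal baselines the group difference is 0 at intake and .30 at week 12, so the two-wave average is .15.
- First reading: .15/.1492 = 1.005; power 17% (normal) or 15% (10 df).
- Second reading: .15/.1189 = 1.26; power 24% or 21%.

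**5. Check against the plan's Aim 3 figure.** For two equal groups d = 2r/√(1 − r²), so r = .21 gives .42/.978 = .43. The design effect is 1 + 40.67 × .05 = 3.03 and effective N is 500/3.03 = 165. The detectable r is tanh(2.802/√(164.8 − 3)) = .22, against .125 without clustering. The plan's r = .21 therefore behaves like a site-clustered group difference and agrees with step 3.

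**The case against.** The strongest reply is that no printed figure is shown to be miscalculated. The clinician d = .46 reproduces before dropout, and the client d = .30 is conservative if it is a change effect with no variance in change. The plan never says that d = .30 belongs to the Aim 3 model, and it gives Aim 3 its own, larger figure. If a group-by-time term was intended, the 15–17% power does not apply. All of this stands. It makes the H1b problem a missing specification, not an arithmetic error, but it does not rescue the summary sentence or the statement in C12a.

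Three stronger readings are tempting:
- A reader might infer that d = .46 and d = .30 assumed almost no site variance in change. The documents do not show this. That they are change effects is itself inferred from the growth-model metric, and person-level variance in change could account for the client figure equally well.
- A reader might take .46 as the corrected value of .30. They are on different scales: one is a two-wave mean difference, the other, as read here, a difference in change. With equal baselines, .42–.46 on the group term corresponds to a week-12 difference of about .84–.93.
- A reader might say that d = .30 and r = .21 also breach the plan's definition of small. The plan prints benchmarks only for κ². The conversion of r to d also assumes two equal groups, whereas Aim 3 enters session counts as well.

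**Conclusion.** The concern holds in this form. Two contradictions need no modelling: client κ² = .10 against a printed medium of .09, and a small effect in C12a against d = .46, called medium, in C13a. H1b has no Aim 1 model, and d = .30 cannot be read as the detectable effect of the only depression model written. That model's group term has a detectable two-wave mean difference of about .42 (normal) or .46 (10 df), or .33 and .37 on the other ICC reading. Its power for a .30 difference in change is about 15–17%, or 21–24%.

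The sizes rest on equal sites, two waves, equal baselines for the .15 shift, and the absence of a group-by-time term as the text stands. The point affects how results are interpreted, not recruitment.

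**What to change.** 1. In the C13a summary, replace the claim about small client effects with the actual detectable values. In C12a, replace the reference to a small effect with d = .46 (medium).
2. State which model and which term test H1b.
   - If it is group by time, add that term to the written depression model and label d = .30 as the detectable difference in change.
   - If it is the group term as written, do not quote d = .30 for it. Report about .42 (normal) or .46 (10 df) if the ICC is a share of total variance, or .33 and .37 if of between-person variance. State which ICC definition applies. Label the value a two-wave mean difference, equal to a week-12 difference about twice as large if baselines are equal.
3. For the Aim 1 simulation, name the tested contrast, the number of waves and every variance component, including any person or site variance in change. Take these from the simulation itself; they cannot be inferred from the printed figures.

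The cost is text and restated figures, with no added sites, clinicians or clients. The downside is a less favourable statement of client sensitivity.
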